Breathing Counts
NCT03065205
Protocol version date 12.18.17

COMIRB Protocol

COLORADO MULTIPLE INSTITUTIONAL REVIEW BOARD
[name] [contact] [contact]

Protocol #: 16-1845

Project Title: Breathing Counts

Principal Investigator: [name]

Version Date: 12-18-17

I. Hypotheses and Specific Aims:

Adherence to asthma medications has been associated with good asthma control in children¹, however adherence to asthma medications is poor.² Children who are hospitalized due to their asthma are at a significantly high risk of re-hospitalization³, and represent a particularly high risk group. Successful control of asthma in a high-risk population requires a network of care providers who communicate relevant up-to-date information and support asthma control. Additionally, lay health worker interventions have been shown in some cases to decrease missed school days and parental work days.⁴ We propose to evaluate the efficacy of an asthma navigator program in a high-risk population of patients at Children's Hospital Colorado. We will evaluate the ability of the program to improve health outcomes of children who have asthma and who are at high-risk of re-hospitalization. The project will also evaluate the ability of the navigator program to increase the number of stakeholder communications amongst school nurses, program navigators, physicians, caregivers and children.

Specific Aim 1: Evaluate whether or not the addition of an asthma navigator to the current clinical standard of care will lead to sustainably increased levels of adherence compared to historical rates.

Hypothesis: By providing up to date adherence rates to the patient's medical care team and by addressing patient identified barriers, we hypothesize that the addition of an asthma navigator to the standard of care at Children's Hospital will increase asthma medication adherence rates, and that these adherence rates will be sustained over the 3-6 month monitoring period.

Specific Aim 2 Evaluate whether or not the addition of an asthma navigator results in increased levels of communication between PCPs, specialty providers and school nurses.

Hypothesis: The addition of an asthma navigator will result in increased emails and general communication between various providers in a patient's care team.

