	Outcome Measure	Visit 1 (admission visit)	Visit 2 (2 months)	Visit 3 (4 months or end of study)	Visit 4 (6 months or end of
--	-----------------	---------------------------------	-----------------------	--	-----------------------------------

					study)
Aim 1	Adherence (continually monitored during trial)		X	X	X
Aim 2	Communication among providers	X			X
Aim 3	Asthma Related Health outcomes	X	X	X	X

- a. Adherence- measured on adherence monitoring devices. The rate of daily prescribed controller medication use will be monitored. For example, if an individual is prescribed two doses per day and the monitoring device records one doses, then the daily adherence measure will be 1/2 or 50%. The outcome measure will be continuously gathered via the Propeller Health monitoring device ® (Madison, WI). Rate of monthly adherence will be calculated between study visits,
- b. Communication between providers. Communication between providers will be measured in a number of ways. Providers include nurses, parents, physicians and patients. In order to measure any change in communication the following communication metrics will be monitored.
 - i. Number of emails sent between providers will be assessed if email is used as the primary means of communication.
 - ii. A subset of provider teams will possibly be enrolled in asynchronous communication monitoring. This is a method of HIPAA compliant messaging, which involves providers utilizing an application or website, and communicating securely within that platform. We plan to utilize the Stich platform, which is marketed as HIPAA compliant (<https://www.teamstitch.com>). We are currently on a waiting list to possibly test the technology.
 - iii. Providers will be surveyed before and after the intervention to determine if they felt that the navigators adequately improved communication regarding specific patient related issues.
- c. Other asthma related outcomes including asthma control test, symptom assessments, asthma related readmissions or revisits, missed school days, and provider satisfaction.
 - i. Asthma Control Test, a self (or in the case of this study, phone administered)-administered questionnaire with 5 questions which summarizes asthma control, will be used to record asthma control in children 12 or older.
 - ii. Childhood Asthma Control Test (or in the case of this study, phone administered), a parent and child administered questionnaire, will be used to record asthma control for children 6-11 years of age.

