 - iii. Pediatric Inhaler Adherence Questionnaire, a self (or in the case of this study, phone administered) survey of barriers to medication adherence
 - iv. Parent attitudes towards medications and barriers to adherence.
 - v. Changes in adherence barriers and behaviors to improve adherence over time
 - vi. The number of asthma related readmissions or revisits between study visits will be self-reported.

- vii. The number of missed school days between visits will be self-reported.
- viii. Provider satisfaction will be recorded using the pre-post surveys

B. Description of Population to be Enrolled:

- a. Children admitted to Children’s Hospital Colorado inpatient or emergency department with a primary diagnosis of asthma exacerbation.
 - i. Inclusion criteria-patients
 - 1. Age 6-17 years
 - 2. On a controller medication at baseline
 - ii. Inclusion criteria-providers
 - 1. Aged 18-70
 - 2. Caring for a patient that is enrolled in the study
 - iii. Exclusion criteria
 - 1. Primary language other than English or Spanish (smartphone application only available in these languages)
 - 2. Homeschooled or not in school
 - 3. Significant developmental delay, cystic fibrosis, interstitial lung disease, tracheostomy/ventilator dependence
 - 4. Following up with a pulmonary or allergy provider outside of the CHCO system

C. Study Design and Research Methods

The proposed study is a single center trial at Children’s Hospital of Colorado, designed to evaluate the effects of a navigator program on medication adherence, provider communication and other asthma related health outcomes. Participants will be recruited from the population of patients between the age of 6 and 17 years admitted to Children’s Hospital Colorado inpatient or emergency department with a primary diagnosis of asthma exacerbation. Investigators plan on a one-year enrollment period and will follow each study participant for 3-6 months.

Recruitment

Upon admission hospital staff will identify potential participants based on the admission medical record. Patients will be approached by research staff and asked if they would like to participate in the study. A member of the research team (principally, the research coordinator) will do the recruiting. The research coordinator will explain the study and enroll subjects. Estimated duration is 45-60 minutes depending upon the patient.

Consent/Assent

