At the time of enrollment, patients will be asked for permission to contact the child's primary care provider and school nurse. If these providers agree to participate in the study, surveys will be sent to all providers of patients (PCPs, school nurses and specialists) to determine if they found the navigator to be helpful, and to see if communication increased due to the intervention. Additionally, the research coordinator will be monitoring the provider portal to ensure that patients' devices are regularly syncing with their phone's Bluetooth, and contact any patients whose devices are not syncing normally. At the study's conclusion, we will plan to have the families return the devices to the research coordinator via US mail. After the conclusion of the study, families will be contacted by the research coordinator to ask if they would be willing to evaluate the navigator via the PSN-I navigator assessment tool. The navigator assessment tool will be used to evaluate utility of the navigator themselves. This is a tool that has been utilized previously in this context to evaluate efficacy of navigator programs. This will only be evaluated at the end of the study. There will be no reimbursement for time for this last survey.

If a patient is having difficulties with syncing their sensors to their phone, we will provide them with a hub to collect the sensor data.

D. Description, Risks and Justification of Procedures and Data Collection Tools:

There will be no medical procedures done during this study. The data collection will occur via surveys, and data collected from the adherence devices. Risks of data collection include accidental disclosure of information, though steps will be taken to prevent this. Also, there is a GPS capability of the devices, so there is a risk of disclosure of patient's location patterns.

E. Potential Scientific Problems:

We are aware that we are underpowered to fully evaluate some of the outcomes that we are interested in obtaining. Additionally, we are limited to single group analysis by request of the funding agency (rather than also having a control group), so we are limited in our ability to make full comparisons. However we would like to undertake this study as a pilot evaluation for the use of the asthma navigator in this population, utilizing adherence monitoring technology to better understand the influence of these evaluations.

F. Data Analysis Plan:

Analysis plan

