Demographic information including age, sex, race, and other baseline clinical information upon recruitment including duration of asthma, C-ACT score, ACT score, asthma symptoms, lung function, prescribed medication, and asthma related health care use in the previous year will be obtained at enrollment. The distributions of outcomes will be examined for normality using the Anderson-Darling Test. Dependent upon the distribution we will use the Wilcoxon rank-sum test, Mann-Whitney U test or paired T-test to test for significant changes in outcomes during the study period. Longitudinal patterns of adherence will be examined graphically.

Monthly rates of adherence, asthma symptoms, asthma control scores and monthly missed number of school days and number of hospitalizations will be calculated by study arm. Survey information from patients, caregivers, physicians and navigators on the navigator intervention will be reviewed by study staff and summarized qualitatively. Number of rehospitalizations will be obtained via chart review at 1 month, 6 months and 12 months post hospitalization.

The cost-effectiveness of the navigator intervention will be summarized based on medical resource utilization (direct) and loss of productivity (indirect). Medical resources utilization will include medical care resource utilization, asthma medication variables, navigator time and salary, while loss of productivity will be measured using the number of hours caretaker missed work due to participant's asthma, number of hours dependent participant missed school due to his/her asthma, and number of hours independent participant missed work due to his/her asthma. Unit costs will be applied to healthcare resources and loss of productivity and summed to obtain total costs for each subject. Average costs for the study group will be presented.

Power and Sample Size

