The study is limited by time frame and funding for a one year recruitment period. The primary goal of the study is to provide preliminary information on the effect of a navigator program on the patient and caregiver response to asthma disease control. As a pilot and feasibility study, investigators have chosen to enroll a total of 100 patients and up to 400 providers. Through past clinical experience, we know that some months of the year are higher risk for asthma exacerbations, so we expect to screen more patients during the fall and winter than summer or spring. Considering the variable clinical case load Investigators plan on enrolling an average of 10 participants per month. Anticipating an enrollment rate of approximately 20% (in 2015, there were >600 asthma related admissions at Children's Hospital Colorado), investigators state they should be able to enroll up to 100 patients within one year. We plan to enroll up to 4 providers per patient with a simple pre-post survey as well.

The primary hypothesis of interest is to test whether change in adherence rates are different from zero. The smallest detectable difference was based on a paired sample t-test between pre and post adherence scores with a Type I error rate of 0.05 and 90% power. Based on previous studies⁸, investigators assumed a mean adherence rate of 50% with a standard deviation of 22%.

Table X:	
N	Δ
100	8%
65	10%
30	15%

Table X lists the smallest detectable difference (Δ) for by sample size. For the primary aim investigators will be able to detect a change of 8% or more in percent adherence during the study period with the available 100 patients.

F. Summarize Knowledge to be Gained:

- a. **Utility of an asthma navigator in addition to electronic adherence monitoring in improving adherence to asthma medications**
- b. **Utility of an asthma navigator in improving communication amongst all of a patient's medical providers**
- c. **Utility of an asthma navigator in improving other asthma control related outcomes.**

Asthma Control Classification

Control is computed based on taking the entry with the worst outcome in the following age-based tables:

Asthma Control Classification (Age 5-10)

(Age 5-11)	Asthma	Control	Classification
	Well controlled	Not well controlled	Very poorly controlled
Symptoms (manually entered)	≤ 2 days/week but not more than once on each day	> 2 days/week or multiple times on ≤ 2 days/week	Every day in previous week

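### As described, the provider pre-post survey yields no testable change in communication for Aim 2, and its stated analysis is a qualitative summary that does not list school nurses

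*Combined protocol and SAP*

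**What the plan says.** Specific Aim 2 (Section I) asks whether adding a navigator "results in increased levels of communication between PCPs, specialty providers and school nurses". Table 1 in IV.A has a row for this aim, "Communication among providers", marked at Visit 1 and Visit 4. IV.A.b introduces three metrics: "In order to measure any change in communication the following communication metrics will be monitored". They are (i) emails between providers, (ii) messages on a secure platform, and (iii) a survey: "Providers will be surveyed before and after the intervention to determine if they felt that the navigators adequately improved communication".

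The survey comes up in four other places:

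- IV.C, Study Design: "surveys will be sent to all providers of patients (PCPs, school nurses and specialists) to determine if they found the navigator to be helpful". The sentence adds a second purpose, to learn whether communication rose because of the intervention.
- IV.A.c.viii: "Provider satisfaction will be recorded using the pre-post surveys".
- IV.F, Analysis plan: "Survey information from patients, caregivers, physicians and navigators on the navigator intervention will be reviewed by study staff and summarized qualitatively".
- Power and Sample Size: "We plan to enroll up to 4 providers per patient with a simple pre-post survey as well".

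The Analysis plan also has a general sentence: changes in outcomes over the study will be tested with a Wilcoxon rank-sum, Mann-Whitney U or paired t-test, depending on the distribution. It then names the outcomes to be calculated: adherence, symptoms, control scores, missed school days and hospitalizations. Communication is not among them.

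**The concern.** A before-and-after survey is useful when the same quantity is asked about twice. The content described here is an evaluation of the navigator, which a provider can give only once the navigator has been at work. The before round then has nothing to contribute to a contrast, and the survey becomes an after-only opinion about the programme, summarised by the study's own staff.

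Aim 2 is a question about increase, and the study has one group. Without a baseline measure of communication there is nothing to compare the after value with. A baseline that was not collected before the navigator started cannot be reconstructed later.

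**Working it through.** **1. The plan's own figure.** Power and Sample Size gives 100 patients and up to 4 providers each: 100 × 4 = 400, which matches the stated maximum. This is the only figure given for the survey. There is no effect size, standard deviation or response rate, so no power calculation decides the point; it turns on what is measured and how it is analysed. The number of distinct people will be below 400 if one provider serves several enrolled children. That is likely for specialists, because IV.B excludes children followed by pulmonary or allergy providers outside the hospital's system.

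**2. Can each stated purpose be answered in the before round?**

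| Stated content | Where | Answerable before the navigator starts? |
|---|---|---|
| Did the navigators improve communication? | IV.A.b.iii | No |
| Was the navigator helpful? | IV.C, Study Design | No |
| Did communication rise because of the intervention? | IV.C, Study Design | No |
| Provider satisfaction | IV.A.c.viii | Unclear; the plan does not say satisfaction with what |

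No item on the level of communication, such as how often providers are in contact or how adequate that contact is, is described for either round.

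**3. What the analysis does with the answers.** The one sentence specific to surveys calls for a qualitative summary, which produces no change score. Set beside the other sections:

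- Aim 2 names PCPs, specialty providers and school nurses.
- IV.C surveys PCPs, school nurses and specialists.
- The IV.F survey sentence names patients, caregivers, physicians and navigators.

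School nurses appear in the first two lists and not in the third.

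**4. Whether the general test sentence fills the gap.** Communication is a Table 1 outcome at two visits, so the sentence could be meant to include it. But it needs a variable, and the plan defines no survey item or score. Two of its three named options, Wilcoxon rank-sum and Mann-Whitney U, are the same test and are for independent samples, so they do not suit a before-and-after comparison in the same providers.

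**5. Whether the other Aim 2 metrics secure a baseline.**

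- Email counts (IV.A.b.i) apply only if email is the main channel.
- Platform messages (IV.A.b.ii) are possible, for a subset of teams, and the study is on a waiting list for the product.
- The navigator's tally of communications (IV.C) is described during the programme. No count from before it is described. The navigator also emails monthly adherence reports to the PCP, specialist and school nurse, and no rule says whether these are counted.

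The survey is therefore the only unconditional Aim 2 metric with a described round before the intervention. Section E confirms there is no control group. Aim 1 at least refers to historical rates; Aim 2 offers none.

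**The case against.** The strongest reply is that the plan states why providers are surveyed, not what each round asks. The questionnaire is not in the documents. It may contain communication-level items asked twice, with the difference answering the stated purpose, and the lead-in to IV.A.b fits that reading. This stands. A reader might infer that the survey cannot test Aim 2, or that no provider can supply a before-and-after change. Both treat unseen item wording as known, and the documents do not support them.

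Second, the qualitative sentence concerns survey information about the navigator intervention and includes patients, caregivers and the navigators themselves. It may cover only opinions of the programme and leave the Aim 2 outcome to the general test sentence. This is a fair reading, so it would be too strong to say that the survey analysis is certainly qualitative only. It does not remove the gap, because no survey variable is defined for that sentence to test.

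Third, school nurses are missing from one analysis list, not from data collection: IV.A.b counts nurses as providers and IV.C surveys them. A reader might infer that their data are excluded; nothing says so.

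Fourth, Aim 2 does not rest on the survey alone, the primary hypothesis is adherence, and the study is a single-group pilot that acknowledges limited power and comparisons. This lowers the priority. Pilot status excuses low power, but it does not explain a before round whose described question has no answer at that time.

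**Conclusion.** The concern holds in a limited form: as described, the provider survey gives no testable change in communication for Aim 2. Its stated communication content has no meaningful value before the intervention, and its specific analysis is a qualitative summary that does not list school nurses. The plan leaves this ambiguous; the documents do not show that Aim 2 is untestable.

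The reach is one of three specific aims and a survey of up to 400 providers. No bias, error rate or loss of power can be calculated, because the plan gives no survey measure to calculate it from. The conclusion assumes that the sections describe the survey's communication content fully. If the questionnaire already repeats communication-level items, what remains is to state those items and their analysis and to add school nurses to the list.

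This should be fixed, but it does not threaten the primary aim.

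**What to change.** In IV.A.b.iii:

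- Ask each PCP, specialist and school nurse the same neutral items before and after: frequency of contact with the other providers about the child over a fixed recall period, and adequacy of that contact.
- Put items that evaluate the navigator, including satisfaction with the navigator, in the after round only.
- If such communication items already exist, state them.

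In the Analysis plan of IV.F:

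- Name PCPs, specialists and school nurses in place of physicians alone.
- Analyse the closed items as paired change by provider group, with a method that allows for providers who serve several enrolled children, for example a mixed model with a provider effect.
- Keep the qualitative summary for free text.

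The cost is survey wording and a few sentences, with no added staff or visits. There are two downsides. Providers already surveyed with navigator-evaluation items alone in the before round would contribute after data only. A specialist newly assigned at the follow-up visit 2-4 weeks after discharge may have little or no earlier contact to report, so the items need a zero and a not-applicable response. The paired change would still be uncontrolled, and the report should say so.

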We will obtain a signed parental permission form and an age-appropriate assent form for participants younger than 18 years. Consent will be obtained by a member of the research team (principally, the research coordinator or a research assistant). It will be made clear to patients that the research team is not part of the treatment team.

Study Design

We plan to enroll a total of 100 patients. and up to 400 providers. Patients enrolled will be provided and trained on using the adherence monitoring prior to discharge (sensors will be placed on discharge controller and quick-relief medication). Participants will also be enrolled in the smartphone application that will give them feedback about their medication usage. Once enrolled in the application, patients will receive push notification reminders to use their medications, as well as be able to access their adherence information in real time. Caretakers will also be given the

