option to have access to their child's adherence information. The smartphone application also has portions dedicated to education about asthma triggers. Patients will be set up with a pulmonary or allergy follow up within 2-4 weeks of discharge. Patient's pulmonary or allergy providers will also be enrolled in the propeller health system, with access to the propeller health dashboard. Once providers receive access, they will be able to log-in and view all of their patients in list format. They will be able to see up to the minute data on patient adherence at any time that they choose to log-in to the dashboard. Providers will also receive email notifications if their patient has not used their controller medications for 7 days, or if their patient has had a significant increase in quick-relief medication use, indicating a worsening of asthma status (see figure 1 below). Patients will be monitored for a total of 3-6 months. The asthma navigator will contact the families at 2, 4 and 6 months post-enrollment, and discuss the patient's recorded adherence with the families. If a patient is enrolled for 4-5 months, we will discuss adherence at 2 and 4/5 months. If a patient is only enrolled for 3 months, we will discuss adherence at 2 and 3 months. Additionally, they will discuss any barriers to adherence that the family may be experiencing, and make referrals to social work as necessary, as well as attempt to brainstorm ways to improve adherence with the families. Additionally, the asthma navigator will collect each patients' adherence data and create an adherence report, which will be distributed on a monthly basis to the patient's primary care provider, pulmonary/allergy provider, and school nurse via email. The asthma navigator will be monitoring communications between the providers and marking the numbers of communications.

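### Missed school days are analysed as a monthly number with no scheduled-school-day denominator, so a school break alone can move a child's figure.

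*Combined protocol and SAP*

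**What the plan says.** Section IV.A (Outcome Measure(s), item c.vii) defines the outcome: "The number of missed school days between visits will be self-reported". The table of outcomes in the same section has one row, "Asthma Related Health outcomes", for the whole Aim 3 group, marked at all four visits, including the admission visit.

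Section IV.C sets the time frame: "Investigators plan on a one-year enrollment period and will follow each study participant for 3-6 months". Families are contacted at 2, 4 and 6 months, with shorter schedules for those followed for less time, for example: "If a patient is enrolled for 4-5 months, we will discuss adherence at 2 and 4/5 months".

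Section F (Data Analysis Plan) calculates a monthly figure for missed school days, alongside adherence, symptoms, control scores and hospitalizations. It provides for a paired t-test or a rank test of change over the study. It names no specific contrast for missed school days and no adjustment for season or school calendar.

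On school status, section IV.B excludes a child who is "Homeschooled or not in school". No section asks how many days school was in session during an interval.

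**The concern.** A child cannot miss school when there is none. Expected missed days in an interval are the absence risk per school day times the number of school days in it. The plan records the product but not the second factor, so a fall could mean better asthma or simply summer. Converting to a monthly figure does not help, because a month of holiday and a month of term count alike.

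Background and Significance treats missed school as a consequence of poor asthma control, so readers will take a change in this outcome as a change in health. If scheduled days are not collected, the analysis cannot separate the two explanations.

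**Working it through.** The documents give no rate, standard deviation or target for missed school days, so there is no stated figure to reproduce. The check is an illustration with a child whose health does not change.

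**Inputs from the documents.** Self-reported count between visits (IV.A); monthly scale (F); contacts at 2, 4 and 6 months, one-year enrolment, 3 to 6 months of follow-up (IV.C).

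**Assumptions, not in the documents.** School share by month: June and July 0, August 0.5, all others 1. Constant absence risk r per school day; D school days in a full school month. Month 1 is the enrolment month.

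**Formula.** Expected missed days per month in an interval = r × D × s, where s is the mean school share over the interval. With r and D fixed, the ratio of months 5-6 to months 1-2 is s(5-6) / s(1-2).

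| Enrolled | s, months 1-2 | s, months 5-6 | Ratio |
|---|---|---|---|
| January | 1.00 | 0.50 | 0.50 |
| February | 1.00 | 0 | 0 |
| March | 1.00 | 0.25 | 0.25 |
| April | 1.00 | 0.75 | 0.75 |
| May | 0.50 | 1.00 | 2.0 |
| June | 0 | 1.00 | undefined |
| July | 0.25 | 1.00 | 4.0 |
| August | 0.75 | 1.00 | 1.33 |
| September-December | 1.00 | 1.00 | 1.0 |

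Eight of the 12 enrolment months give a ratio other than 1, in both directions.

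**A different calendar.** Now assume weekdays only; breaks 1 June-15 August, 22-26 November, 20 December-4 January and 20-27 March; 61-day intervals; enrolment on the first of the month; and a 5% absence risk. Missed days per month = 0.05 × school days / 2.

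- February enrolee: 37, 43 and 0 school days give 0.925, 1.075 and 0.
- April enrolee: 43, 0 and 33 give 1.075, 0 and 0.825.
- July enrolee: 11, 43 and 33 give 0.275, 1.075 and 0.825. The ratio of last to first interval is 33/11 = 3.0, against 4.0 above.

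The exact ratios depend on the calendar, but the pattern does not.

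**What the monthly scale does correct.** At 5% and an assumed 21 school days per month, 1-, 2- and 3-month intervals give counts of 1.05, 2.10 and 3.15, but 1.05 per month in each. Unequal visit spacing is handled. School breaks are not.

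**Group level, first calendar.** With even enrolment and everyone reaching month 6, the 12 shares sum to 9.5 for months 1-2 and to 9.5 for months 5-6. Both means are 9.5/12 = 0.792 and the ratio is 1.00.

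That balance needs both conditions. Suppose enrolment is even but only the first nine enrolment months reach month 6 (an assumed closing rule). If enrolment starts in August, the sums are 8.75 and 6.5, ratio 6.5/8.75 = 0.74. If it starts in April, they are 6.5 and 8.75, ratio 8.75/6.5 = 1.35. These two cases show only that the direction is open. They do not estimate the bias in this study.

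**After the fix.** The February enrolee's expected missed days per scheduled day are 1.85/37 = 5% and 2.15/43 = 5%. The third interval is 0/0, which is missing and not zero.

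**The case against.** The strongest reply is that the group result may be unaffected. With even enrolment and complete six-month follow-up the distortion cancels, and this is one self-reported item in a pilot that already admits limited power and the lack of a control group (section IV.E, Potential Scientific Problems). That stands, and it keeps the point minor. It does not remove the defect: neither admission covers a missing denominator, which can be supplied within a single group.

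Four stronger readings are tempting, and the documents do not support them.

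- *The outcome has no reference period.* It has one: the interval between visits, put on a monthly scale. What is missing is narrower, namely any look-back before Visit 1. The mark at Visit 1 in the outcome table does not contradict this. It covers a mixed group of outcomes, some of which, such as readmissions and provider satisfaction, have their own timing.
- *The bias favours the programme, because more children enter in fall and winter.* The Power and Sample Size section expects more screening in those seasons. It gives no enrolment ratio, and no section gives a closing rule. Any group-level figure therefore rests on assumptions about both, as well as on the school calendar.
- *Children followed for only three months escape the problem.* On the first calendar, the ratio of month 3 to months 1-2 is 0 for April and May enrolees, 1.33 for August, 4.0 for July and undefined for June. It is 1.0 for the other months.
- *The same flaw affects control scores first measured at admission.* Recovery after an exacerbation is a separate matter, unrelated to school days, and section IV.E already concedes the single-group limit.

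The exclusion of children not in school is no answer either, since it does not deal with breaks during follow-up.

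**Conclusion.** The concern holds, as a minor one. The plan as written gives a missed-school-days figure that mixes the school calendar with the child's health. That no denominator is recorded follows from the text alone. The size rests on the assumed calendar and a constant absence risk: for individual children the apparent change runs from a fall to zero to a fourfold rise. For the group, the documents support no number and no direction.

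**What to change.** 1. Record the number of scheduled school days in each interval, taken from the school's calendar. This need not go through the school nurse, whose involvement depends on family permission and the nurse's own agreement (IV.C).
2. Analyse missed days per scheduled school day. A simple per-child rate in the test of change already planned is enough. A count model with log scheduled days as offset, allowing for repeated intervals per child, is an alternative.
3. Set intervals with no school days to missing, not zero.
4. Name Visit 1 to Visit 2 as the first interval and count it from discharge, because no look-back before Visit 1 is defined and days lost to the index admission would inflate the starting rate.

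The cost is one added field and some wording. On the first calendar, June enrolees have no first interval (1/12 = 8.3% with even enrolment, about 8 of 100 children). April enrolees lose months 3-4 and February enrolees lose months 5-6. The offset model still uses these children's other intervals. Rates from intervals with few school days will be imprecise, which should be stated. Two limits remain: seasonal variation in asthma risk is not removed, and the first interval already includes programme exposure, since "sensors will be placed on discharge controller and quick-relief medication". The contrast therefore describes change during the programme, not its full effect.
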